(18) Study vaccine has to be administered by study staff otherwise not involved with study conduct to keep the study observer-blinded. Subjects enrolled in the Run-in phase should be observed for at least one hour, subjects enrolled in the Main Study phase should be observed for at least 30 min after vaccination for treatment of any immediate reactions.

(19) Except for Visit 1: Body systems for which the subject reports any symptoms should be evaluated and relevant abnormal findings documented as AEs. At vaccination days the symptom-driven physical exam is to be performed before administration of the vaccination.

(20) If subject has any complaints after vaccination, a second symptom-driven physical examination will be performed by the investigator prior to discharge.

(21) The injection site of previous injections should be evaluated by study staff prior to the next vaccination.

(22) At Visit 1, the subjects will be provided with thermometer and measuring tapes. The subjects will assess solicited local and systemic AEs themselves over a period of seven consecutive days after each vaccination.

(23) Unreturned Subject Diaries/ Memory Aids should be collected at the Early Termination Visit. For Early Terminations prior to Visit 4, the previous injection site should be inspected.

(24) AEs, SAEs and AESIs will be collected throughout study conduct. Symptoms noted at Visit 1 (prior to vaccination) are not considered adverse events but will be recorded as medical history.

(25) Women of non-childbearing potential and male subjects.

(26) If applicable, HIV test, Lyme borreliosis screening test, serum pregnancy test, clinical chemistry tests, hematology tests, and coagulation tests performed at the study site within the study VLA15-202 are acceptable for study VLA15-201 if within the specified visit window. As such, if test results are available, respective blood samples do not need to be collected again for the present study. Similar, if applicable, a baseline serology sample collected at the study site within the study VLA15-201 if within the specified visit window.

* Functional antibody analysis will be provided using a serum bactericidal assay.

Adapted from:
 STAT03_A Statistical Analysis Plan
 Version 6.0, Effective Date 16-Feb-2018
 Confidential and intellectual property of [REDACTED]

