6.1.2.1 General Principles for Analysis of Adverse Event

- In general, for tables summarizing solicited AEs, only the Subject Diary will be used. For tables for all AEs (solicited and unsolicited) in general the unsolicited AEs will be taken from the eCRF section “AE-log” and the solicited AEs will only be taken from the eCRF section “Subject Diary”.
- Tables showing “severe” events will include events with grade 3 or 4 (or missing grade).
- For tables by maximum severity and worst causality, subjects will only be counted once in highest grading category and events will be counted in each reported grading category.
- Percentages in tables that do not present data by time periods are based on N (treatment group totals).
- For the IA Day 85 all AEs from the eCRF section “Subject Diary” and AEs from the eCRF section “AE log” that started up to Day 85 (Visit4) will be analyzed. It will be stated in the table header that AEs up to Day 85 will be analyzed.
- For the IA Day 236 all AEs from the eCRF section “Subject Diary” and AEs from the eCRF section “AE log” that started up to Day 236 (Visit 6) will be analyzed. It will be stated in the table header that AEs up to Day 236 will be analyzed.
- AEs in the AE log will be considered to have started up to Day 85 if the start date of the AE is before or on study Day 85 (Visit 4). In case of an incomplete start date where it cannot clearly be decided if the AE started up to Day 85 or not, the AE will be considered to have started up to Day 85. The derivation of AEs started before or on Day 236 will be determined analogously.
- For analysis of non-serious solicited (eCRF section “Subject Diary”) and non-serious unsolicited (eCRF section “Adverse Event log”) AEs only AEs for which the question “Serious adverse event” was ticked with “no” in the eCRF will be included. Adverse Events will only be included for this analysis if their occurrence by PT in at least one treatment group in the Safety Population is 5% or over 10%, respectively.

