6.1.2.2 Principles for Solicited Adverse Events

Solicited AEs comprise reactions at the injection site or systemic reactions that are typical for vaccinations:

- Solicited local AEs: pain, tenderness, induration/ hardening, swelling and erythema/ redness
- Solicited systemic AEs: headache, myalgia (muscle pain), arthralgia (joint pain), fever (oral body temperature), flu-like symptoms, nausea, vomiting and fatigue
- Solicited AEs are per definition regarded as related to IMP.
- For tables that summarize solicited AEs over several diary days / diary periods from the Subject Diary, the worst severity of all diary days / diary periods is taken as the events severity.
- Percentages in tables for solicited AEs by diary period /diary day are based on the number of subjects with available information (diary completed or symptom present on at least one day). In particular, if a

symptom was not assessed at a certain diary day and the symptom is reported as not present on the other days, the subject is not included in the table of the respective symptom and diary period.

- For the derivation of the duration of solicited Adverse Events by symptom and vaccination period the difference of the first occurrence and the last occurrence of the concerning event in the respective vaccination period will be taken, no matter if the event is continuous or not. Therefore, also the end-date if ongoing after day 6 will be considered. If the AE was ongoing after day 6 but has a missing or incomplete end-date, the date of last attended visit will be used as end date.
- For swelling, redness and induration, the maximum diameter per diary period in cm will be derived as taking the maximum of all diameters reported in that period for that symptom and converting via $[cm] = [in] \times 2.54$.
- The maximum body temperature per diary period for present symptom fever will be derived as taking the maximum temperature of all temperatures reported in that period and converting via $[^{\circ}C] = ([^{\circ}F] - 32) \times 5/9$.
- Adverse Events from the Subject Diary will be coded according to the table below:

[figure not shown]
Event	SOC name	SOC code	PT name	PT code
Arthralgia	Musculoskeletal and connective tissue disorders	10028395	Arthralgia	10003239
Fatigue	General disorders and administration site conditions	10018065	Fatigue	10016256
Fever	General disorders and administration site conditions	10018065	Pyrexia	10037660

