Table 14.1.4.25:	Subjects with Solicited Local Adverse Events after any Vaccination by Symptom Classified by Maximum Severity (Safety Population)	X		Including statistical test
Table 14.1.4.26:	Subjects with Solicited Local Adverse Events after any Vaccination by Symptom and Age Group Classified by Maximum Severity (Safety Population)	X		Including statistical test
Table 14.1.4.27:	Subjects with Solicited Local Adverse Events after any Vaccination by Symptom and Region Classified by Maximum Severity (Safety Population)	X		Including statistical test
Table 14.1.4.28:	Subjects with Solicited Local Adverse Events after any Vaccination by Symptom and B.b. s.l. serostatus Classified by Maximum Severity (Safety Population)	X		Including statistical test
Table 14.1.4.29:	Subjects with Solicited Systemic Adverse Events after any Vaccination by Symptom Classified by Maximum Severity (Safety Population)	X		Including statistical test
Table 14.1.4.30:	Subjects with Solicited Systemic Adverse Events after any Vaccination by Symptom and Age Group Classified by Maximum Severity (Safety Population)	X		Including statistical test
Table 14.1.4.31:	Subjects with Solicited Systemic Adverse Events after any Vaccination by Symptom and Region Classified by Maximum Severity (Safety Population)	X		Including statistical test
Table 14.1.4.32:	Subjects with Solicited Systemic Adverse Events after any Vaccination by Symptom and B.b. s.l. serostatus Classified by Maximum Severity (Safety Population)	X		Including statistical test
Table 14.1.4.33:	Subjects with Solicited Adverse Events by Vaccination Period (Safety Population)	X		Including statistical test
Table 14.1.4.34:	Subjects with Solicited Local Adverse Events by Symptom and by Vaccination Period (Safety Population)	X		Including statistical test
Table 14.1.4.35:	Subjects with Solicited Systemic Adverse Events by Symptom and by Vaccination Period (Safety Population)	X		Including statistical test

Table 14.1.4.36:	Subjects with Solicited Adverse Events by Vaccination Period Classified by Maximum Severity (Safety Population)	X		Including statistical test
Table 14.1.4.37:	Subjects with Solicited Local Adverse Events by Vaccination Period Classified by Maximum Severity (Safety Population)	X		Including statistical test
Table 14.1.4.38:	Subjects with Solicited Systemic Adverse Events by Vaccination Period Classified by Maximum Severity (Safety Population)	X		Including statistical test

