Listing 16.2.1.4.1.13:	Adverse Events Leading to Withdrawal from Further Vaccination (Vaccinated Subjects)	Patient ID, Group, Adverse event term, MedDRA PT (MedDRA 22.1), MedDRA SOC(MedDRA 22.1), Severity, Causality, Start date, Withdrawn from further vacc. after vacc., Onset (relative to previous vacc.) [days], Estimated Duration of AE (incl. missing stop date) [days]
Listing 16.2.1.4.1.14:	Adverse Events Leading to Withdrawal from the Study (Vaccinated Subjects)	Patient ID, Group, Adverse event term, MedDRA PT (MedDRA 22.1), MedDRA SOC(MedDRA 22.1), Severity, Causality, Start date, Withdrawn from study after vacc., Onset (relative to previous vacc.) [days], Estimated Duration of AE (incl. missing stop date) [days]
Listing 16.2.1.4.1.15:	Adverse Events with Missing Assessment (eCRF Section "AE log") Part I (Vaccinated Subjects)	See Listing 16.2.1.4.1.1
Listing 16.2.1.4.1.16:	Adverse Events with Missing Assessment (eCRF Section "AE log") Part II (Vaccinated Subjects)	See Listing 16.2.1.4.1.8
Listing 16.2.1.4.1.17:	Solicited Adverse Events by Diary Day (Vaccinated Subjects)	Patient ID, Group, Symptom, Present after vaccination, Serious, Medically attended, Taken any medication due to symptom, Withdrawn from further vaccination, Withdrawn from study, Time point, Symptom ongoing after Day 6, Meets FDA Toxicity Grading Scale, Grade per diary day (incl. not present), Size [cm], Oral body temperature [°C]
Listing 16.2.1.4.1.18:	Severe Solicited Adverse Events by Diary Day (Vaccinated Subjects)	See Listing 16.2.1.4.1.17
Listing 16.2.1.4.1.19:	Solicited Adverse Events with Missing Assessments by Diary Day (Vaccinated Subjects)	See Listing 16.2.1.4.1.17
Listing 16.2.1.4.1.20:	Solicited Adverse Events by Diary Period (Vaccinated Subjects)	Patient ID, Group, Symptom, Present after vaccination, Serious, Medically attended, Taken any medication due to symptom, Withdrawn from further vaccination, Withdrawn from study, Onset (relative to previous vacc.) [days], Stop day (relative to previous vacc.) [days], Maximum severity (grade 0-4 and n/p)
Listing 16.2.1.4.1.21:	Severe Solicited Adverse Events by Diary Period (Vaccinated Subjects)	See Listing 16.2.1.4.1.21
Listing 16.2.1.4.2.1:	Hematology Values Outside Normal Range or Meeting FDA Grading Scale for Lab Assessments	Patient ID, Group, Visit, Date, Time, Parameter, FDA Grading, Result, Unit, Lower Limit, Upper Limit, Result (converted), Unit (converted), Lower limit (converted), Upper limit (converted), Out of normal

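### Solicited AE derivations (SAP 6.1.2.2): inclusion of incomplete diaries depends on the outcome, durations are one day short, and missing end dates are closed with no limit

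*SAP*

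**What the plan says.** **Denominator.** SAP Section 6.1.2.2 bases percentages by diary period or diary day on the "number of subjects with available information (diary completed or symptom present on at least one day". It adds that if a "symptom was not assessed at a certain diary day and the symptom is reported as not present on the other days", then "the subject is not included in the table of the respective symptom and diary period". The rule governs Table 14.1.4.34, "Subjects with Solicited Local Adverse Events by Symptom and by Vaccination Period (Safety Population", and likewise Tables 14.1.4.35, 39 and 40. Section 7.1.4 marks all four as including a statistical test. For the tables over all vaccinations, Section 6.1.2.1 applies instead: "Percentages in tables that do not present data by time periods are based on N (treatment group totals".

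**Duration.** Section 6.1.2.2 defines it as the "difference of the first occurrence and the last occurrence of the concerning event in the respective vaccination period", whether or not the event is continuous. An end date after diary day 6 is taken into account. If it is missing or incomplete, the date of the last attended visit replaces it. Section 1.5.2 sets the diary length: "The subjects will assess solicited local and systemic AEs themselves over a period of seven consecutive days after each vaccination". Section 6.1.1 asks for a mean duration in days. Section 7.1.4 lists Tables 14.1.4.46 and 14.1.4.47, whose titles speak of a number of days.

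**Visibility of gaps.** Section 7.2.4 plans Listing 16.2.1.4.1.19, "Solicited Adverse Events with Missing Assessments by Diary Day (Vaccinated Subjects".

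**The concern.** The frequency of solicited events after each and after any vaccination is a secondary endpoint (Section 1.3.2). Three derivation rules behind its tables cause trouble.

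1. Take two subjects who each missed one diary day. The one who reported the symptom is counted, and the one who did not is removed. Only symptom-free subjects can leave the by-period denominator in this way. The tables over all vaccinations keep both subjects, because they use N. For the by-day tables (14.1.4.41 to 43) the rule is unclear: the general sentence covers diary days, but the exclusion sentence names only symptom and diary period.
2. A plain difference of dates loses one day, so the shortest event has no duration at all.
3. Closing an open event at the last attended visit can give a reaction to one dose a length that runs past the following doses. The section does not say whether visits after Day 85 count.

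At stake are the level of the reported per-dose rates, their comparison between groups if diary completeness differs, and the mean durations. The primary GMT analysis does not use these data.

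**Working it through.** The SAP states no figure for these rules, so there is none to reproduce.

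**1. Denominator**

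Inputs:
- N = 210 per main dose group (Section 1.4).
- p, the true rate in a period: assumed.
- m, the share of incomplete diaries: assumed. m1 and m0 are this share with and without the symptom.
- q, the chance that a symptom in an incomplete diary still shows on an assessed day: assumed.

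Rate under the SAP rule = p(1 − m1 + m1·q) / [p(1 − m1 + m1·q) + (1 − p)(1 − m0)].

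With m1 = m0 = m and q = 1 this becomes p / (1 − m(1 − p)):

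| True p | m = 5% | m = 10% | m = 15% |
|---|---|---|---|
| 10% | 0.10/0.955 = 10.5% | 0.10/0.91 = 11.0% | – |
| 50% | 0.50/0.975 = 51.3% | 0.50/0.95 = 52.6% | 0.50/0.925 = 54.1% |

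- Subjects dropped at p = 50%: 105 × 0.05 = 5.25, or 105 × 0.10 = 10.5.
- Equal completeness (m = 10%), true rates 60% and 65%: 0.60/0.96 = 62.5% and 0.65/0.965 = 67.4%. The difference is 4.9 points instead of 5.0.
- Unequal completeness (5% against 15%), both groups truly at 50%: 51.3% against 54.1%, an apparent difference of 2.8 points.
- Reversal: p = 50%, m1 = 15%, m0 = 5%, q = 0.5. SAP rate = 0.4625/(0.4625 + 0.475) = 49.3%. Complete-diary rate = 0.425/(0.425 + 0.475) = 47.2%. Here both are too low, and the SAP rate is the closer one.

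**2. Duration**

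Seven diary days ending with day 6 run from day 0 to day 6.
- Symptom on one day only: 0 − 0 = 0; with one day added, 1.
- Symptom on all seven days: 6 − 0 = 6; with one day added, 7.
- Symptom on days 0 and 6 only: 6 under the rule, a span of 7, and 2 symptom days. A first-to-last span is therefore not a number of days with the symptom.

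**3. Missing end date**

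Vaccinations are on Days 1, 29 and 57, Visit 4 is Day 85 and Visit 6 is Day 236 (Sections 1.2 and 1.5.2). Onset is taken on the vaccination day. The nominal period is 28 days (29 − 1, 57 − 29, 85 − 57).

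| Dose | Closed at Visit 4 | Closed at Visit 6 |
|---|---|---|
| 1 | 85 − 1 = 84 | 236 − 1 = 235 |
| 2 | 85 − 29 = 56 | 236 − 29 = 207 |
| 3 | 85 − 57 = 28 | 236 − 57 = 179 |

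Illustration: 50 events after dose 1, of which 49 average 2 days (assumed) and one is imputed. The mean is (98 + 84)/50 = 3.6 days at Visit 4, (98 + 235)/50 = 6.7 days at Visit 6, and (98 + 28)/50 = 2.5 days if limited to the period.

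**The case against.** **The denominator rule is coherent.** It keeps subjects whose outcome for the period is known: a symptom seen once is a yes, and a complete diary without it is a no. It sets aside those whose outcome is unknown. It is prespecified, and the reversal example shows that it can beat the complete-diary rate. This stands, and it is why the complete-diary rate belongs beside the SAP rate and not in its place. A reader might infer that the bias always runs upward, or that group comparisons are spoiled. The first fails when missed days hide symptoms. The second needs unequal completeness, and nothing in this observer-blind design points to that.

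**The exclusions can be traced.** Section 2.5 requires the number of non-missing observations, and Table 14.1.1.1.5 gives the vaccinations. Their difference is the number of non-evaluable subjects, so it would be wrong to say that exclusions are invisible. But that difference pools missing diaries with incomplete diaries in which no symptom was reported. Listing 16.2.1.4.1.19 works only subject by subject.

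**The lost day cancels between groups, and the table link is inferred.** Both are true. The SAP never says that Tables 14.1.4.46 and 14.1.4.47 carry this derivation. They are simply the only listed tables that appear able to hold the mean duration.

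**The end-date rule is not a contradiction.** A reader might say that a duration defined within the vaccination period cannot outlast it. Section 6.1.2.2 expressly considers end dates after day 6, and the mention of the period can simply say which dose an event belongs to. The weakness is the unlimited imputation. It may look inconsistent to limit imputed dates but not reported ones. A reported date is data, however, whereas an imputed one is an assumption.

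**The median is planned as well.** Section 2.5 requires it, and a rare long value hardly moves it. That softens the third point, but the mean is the measure that Section 6.1.1 names.

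**Conclusion.** The point holds as a minor correction with three parts.

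1. In the four tested by-symptom, by-period tables, inclusion of an incomplete diary depends on the outcome. The inflation of a true 50% to between 51.3% and 54.1% rests on an assumed m of 5% to 15%, on missed days unrelated to the symptom, and on q = 1. With equal completeness the group difference is nearly unchanged. No single rate is unbiased if missed days hide symptoms.
2. On the literal wording, every first-to-last duration is one day short. If the programs already add a day, they depart from the text, so the wording needs correcting either way.
3. The imputed end date has no limit. The 84, 56 and 28 days hold only if visits are cut at Visit 4, which the SAP does not settle. The Day 85 analysis starts only after Visit 6 (Sections 2.1 and 2.14), and the Day 85 rule in Section 6.1.2.1 concerns when events start. If Visit 6 counts, the maxima are 235, 207 and 179 days. How often end dates are missing is unknown.

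Parts 2 and 3 touch only descriptive output that is neither an endpoint nor tested.

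**What to change.** 1. **Rates.** Keep the SAP rate in Tables 14.1.4.34, 35, 39 and 40. Show the complete-diary rate beside it. Per group and dose, also show the number excluded for an incomplete diary without a reported symptom. Note that neither rate is unbiased if missed days hide symptoms. State that by-day denominators are the subjects assessed on that day.
2. **Duration.** Define it as last minus first occurrence plus 1. Title the tables as duration from first to last occurrence, or else count symptom days. Link the derivation to Tables 14.1.4.46 and 14.1.4.47 expressly.
3. **Missing or incomplete end dates only.** Censor at the end of that vaccination period: the next vaccination, or 28 days after the dose if none followed. Report the number imputed and read the median beside the mean. Reported end dates stay as reported. Section 6.1.2.3 sets similar limits only to assign unsolicited events by start date, so the rule has to be written for solicited events.

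The cost is a few lines of SAP text, a small programming change, one more set of percentages and two counts. The complete-diary rate loses reactions reported in incomplete diaries, so it must not stand alone. Censoring shortens the imputed durations, which the reported number imputed makes visible.

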6.1.2.3 Principles for Unsolicited Adverse Events

- AEs in the AE log will be coded using the MedDRA version that is current at time point of data snapshots for the interim analysis. The version used will be indicated in the respective tables and listings and will be documented in the CSR.
- Adverse events in the AE log will be considered related if the causality to IMP is reported as “probable” or “possible” (or missing causality)
- An AE in the AE-log is considered as “leading to withdrawal from further vaccination” if for “action taken on IMP”, “second dose not administered” or “third dose not administered” is ticked.
- An AE in the AE-log is considered as “leading to withdrawal from study” if in section “other action taken” the question “Withdrawn from study”, is answered with “yes”.
- Percentages in tables for unsolicited events or all events (solicited and unsolicited) over the whole study are based on N (treatment group totals).
- For presentation of AEs by vaccination period, unsolicited AEs will be assigned as follows:
 - 1st vaccination period: AE with start date/time at or after date/time of 1st vaccination and before date/time of 2nd vaccination. If no AE start time is given, the AE is included if the start date is at or after the date of 1st vaccination and before the date of 2nd vaccination. If no 2nd vaccination was administered, the date 28 days after the 1st vaccination will be used instead.
 - 2nd vaccination period: AE with start date /time at or after date/time of 2nd vaccination and before date/time of 3rd vaccination. If no AE start time is given, the AE is included if the start date is at or after the date of 2nd vaccination and before the date of 3rd vaccination. If no 3rd vaccination was administered, the date 28 days after the 2nd vaccination will be used instead.
 - 3rd vaccination period: AE with start date /time at or after date/time of 3rd vaccination and not later than 28 days after the 3rd vaccination.
 - If a subject did not receive a certain vaccination, the respective vaccination period will not be defined.

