1.2 Study Design

This is a randomized, observer-blind (subject, sponsor and investigator/ site staff involved in clinical evaluation of subjects are blinded), placebo controlled, multicenter Phase 2 study (see Figure 1).

In the Run-in phase, a total of 120 subjects aged 18 to 40 years were to be randomized stratified by study site 1:1:1:1 to receive VLA15 90 µg w/ alum, VLA15 135 µg w/ alum, VLA15 180 µg w/ alum, or placebo (30 subjects per treatment group) as intramuscular (I.M.) vaccinations on Days 1, 29 and 57. Dosing was to be adjusted by injection volume (see Table 1).

Table 1: Treatment Groups and Vaccinations

Group	Treatment	Injection Volume [mL]	Days of Vaccination
90 µg	VLA15 90 µg w/ alum	0.50	1, 29, 57
135 µg	VLA15 135 µg w/ alum	0.75	1, 29, 57
180 µg	VLA15 180 µg w/ alum	1.00	1, 29, 57
Placebo	PBS	1.00	1, 29, 57

Two safety visits were to be performed after the first vaccination: a safety phone call at Day 4 (i.e. Visit 1a, three days after the first vaccination) and an in-person visit at Day 8 (i.e. Visit 1b, seven days after the first vaccination). After all subjects enrolled in the Run-in phase completed Visit 4 (Day 85, i.e. 28 days after the third vaccination) a Data Safety Monitoring Board (DSMB) reviewed all available safety data up to Day 85 in a scheduled DSMB meeting and gave the recommendation that all treatment groups were safe and well tolerated so far and could be continued in the Main Study phase based on available safety data. After the DSMB meeting, the two higher dose groups (135 µg and 180 µg of VLA15 w/ alum) were selected for further investigation. No safety concerns associated with any of the VLA15 treatment groups were identified by the independent DSMB.

In the Main Study phase, a total of 450 subjects aged 18 to 65 years will be randomized stratified by study site, age group and baseline *B.b. s.l.* serostatus 2:2:1 to receive 135 µg or 180 µg VLA15 w/ alum (180 subjects each) or placebo (90 subjects), as I.M. vaccinations on Days 1, 29 and 57. Subjects will be enrolled in two age groups (18-49 years and 50-65 years) in a ratio of approximately 2:1.

In both study phases, target is to enroll approximately 10 % or more of subjects that are baseline seropositive for *Borrelia burgdorferi sensu latu* (*Bb s.l.*). This is aimed to be achieved through selection of endemic recruitment areas as well as database searches for *Bb s.l.* seropositive subjects.

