2. GENERAL CONSIDERATIONS

2.1 Conduct of Analysis

An interim analysis (IA) on safety and immunogenicity data will be conducted in two parts after the last subject completed Visit 6 (i.e. Day 236). The first part (IA Day 85) will be performed after safety data up to Day 85 have been cleaned and immunogenicity samples of Day 1 and 85 have been analyzed. The first part (IA Day 85) will cover safety data up to Visit 4 (Day 85) and ELISA immunogenicity data from Visit 1 (Day 1) and Visit 4 (Day 85). The second part (IA Day 236) will cover safety data up to Visit 6 (Day 236, i.e. six months after the last vaccination).

Data from selected dose groups in the Main Study and data from respective dose groups from the Run-in phase will be pooled for this and all further analyses.

A preliminary immunogenicity analysis was done prior to the IA D 85 as described above. This analysis was described in a separate analysis plan and covered descriptive immunogenicity analysis of selected time points of subjects from the run-in phase only.

A final data analysis will be conducted once the last subject has completed the study, i.e. Visit 7 (Month 12). As part of this analysis, Serum Bactericidal Assay (SBA) results will be analyzed. Those results will only be available for a subset of subjects, that was randomly chosen from the set of subjects from the main phase who have both a Day 1 and Day 85 immunogenicity blood sample.

It is indicated in Section 7, which Tables, Listings and Figures (TLFs) are provided for IA D85 and IA D236.

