7.1.4 Safety

No	Legend	IA D85	IA D236	Content/Comment
Table 14.1.4.1:	Summary Table of Adverse Events (solicited and unsolicited) (Safety Population)	X	X	Including statistical test • Any AE, related AE, severe AE, related

				severe AE, SAE, related SAE, medically attended AE, related medically attended AE, AE leading to withdrawal from study, AE leading to withdrawal from further vaccination 
 • Any solicited AE, severe solicited AE, solicited local AE, severe solicited local AE, solicited systemic AE, severe solicited systemic AE • Any unsolicited AE, related unsolicited AE, severe solicited AE, related severe solicited AE, unsolicited SAE, medically attended unsolicited AE, unsolicited AE leading to withdrawal from study, unsolicited AE leading to withdrawal from further vaccination, AE of special interest, related AE of special interest
Table 14.1.4.2:	Summary Table of Adverse Events by Age group (solicited and unsolicited) (Safety Population)	X	X	Including statistical test Content see table 14.1.4.1
Table 14.1.4.3:	Summary Table of Adverse Events by Region (solicited and unsolicited) (Safety Population)	X	X	Including statistical test Content see table 14.1.4.1
Table 14.1.4.4:	Summary Table of Adverse Events by B.b. s.l. serostatus (solicited and unsolicited) (Safety Population)	X	X	Including statistical test Content see table 14.1.4.1
Table 14.1.4.5:	Summary Table of Adverse Events (solicited and unsolicited) by Vaccination Period (Safety Population)	X	X	Including statistical test Content see table 14.1.4.1
Table 14.1.4.6:	Subjects with Solicited and Unsolicited Serious	X	X	Including statistical test

	Adverse Events by SOC and PT (Safety Population)			
Table 14.1.4.7:	Subjects with Solicited and Unsolicited Related Serious Adverse Events by SOC and PT (Safety Population)	X	X	Including statistical test
Table 14.1.4.8:	Subjects with Solicited and Unsolicited Medically Attended Adverse Events by SOC and PT (Safety Population)	X	X	Including statistical test
Table 14.1.4.9:	Subjects with Solicited and Unsolicited Related Medically Attended Adverse Events by SOC and PT (Safety Population)	X	X	Including statistical test
Table 14.1.4.10:	Subjects with Solicited and Unsolicited Adverse Events Leading to Withdrawal from Further Vaccination by SOC and PT (Safety Population)	X	X	Including statistical test

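### At IA Day 236, Table 14.1.4.5 is to be headed as covering adverse events up to Day 236, but its vaccination periods close at about Day 85 and no follow-up period is defined

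*SAP*

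**What the plan says.** Section 6.1.2.3 gives the rule for presenting unsolicited adverse events by vaccination period:

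- Periods 1 and 2 run from one dose to the next. For a subject who stops after dose 1: "If no 2nd vaccination was administered, the date 28 days after the 1st vaccination will be used instead". For a subject who stops after dose 2: "If no 3rd vaccination was administered, the date 28 days after the 2nd vaccination will be used instead".
- Period 3 starts at dose 3 and takes events "and not later than 28 days after the 3rd vaccination".
- For doses not given: "If a subject did not receive a certain vaccination, the respective vaccination period will not be defined".

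No period is defined after these three.

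On the second interim analysis, section 2.1 says that it "will cover safety data up to Visit 6 (Day 236, i.e. six months after the last vaccination"). Section 6.1.2.1 includes every adverse event that started by Day 236 and adds: "It will be stated in the table header that AEs up to Day 236 will be analyzed".

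Section 7.1.4 marks Table 14.1.4.5, adverse events by vaccination period, for both IA Day 85 and IA Day 236. It is to include a statistical test and to have the row content of Table 14.1.4.1. It is the only by-period adverse event table marked for IA Day 236. The by-period tables of solicited events (14.1.4.33 to 14.1.4.40) are marked for IA Day 85 only.

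**The concern.** The IA Day 236 version of Table 14.1.4.5 is built from periods that end about where the IA Day 85 analysis ends. Its header would state coverage to Day 236, while its columns or blocks would hold almost nothing with onset after Day 85. A reader of the report could take it as showing no late events by period, when late events have no place in it.

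The time left out is the time that IA Day 236 adds. The events affected are unsolicited ones, including SAEs, AESIs and medically attended events; solicited events come from the diary in the seven days after each dose and fall inside the periods. A difference between groups in late-onset events would have to be read from increments in cumulative tables or assembled from listings. Section 2.15 gives a further reason to see this time separately: phone calls could replace on-site visits after Day 85, so events may have been ascertained differently.

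**Working it through.** **Inputs.** Doses are given "as I.M. vaccinations on Days 1, 29 and 57" (section 1.2). The closing rules are those of section 6.1.2.3. The IA Day 236 cut-off is Day 236 (section 6.1.2.1). The visit window for dose 3 is ±4 days (section 1.5.2), and the per-protocol tolerance is ±10 days (section 2.8).

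**The plan's own figure.** Section 1.2 equates Visit 4, Day 85, with 28 days after the third vaccination: 57 + 28 = 85. This reproduces exactly and is also the nominal last day of period 3. Likewise 236 − 57 = 179 days, consistent with the six months stated in section 2.1.

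**Time in no period, all three doses given.** Uncovered days = 236 − (day of dose 3 + 28).

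| Day of dose 3 | Last day of period 3 | Uncovered to Day 236 | Share of 236 days |
|---|---|---|---|
| 47 (−10) | 75 | 161 | 68.2% |
| 53 (−4) | 81 | 155 | 65.7% |
| 57 (nominal) | 85 | 151 | 64.0% |
| 61 (+4) | 89 | 147 | 62.3% |
| 67 (+10) | 95 | 141 | 59.7% |

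**Early stoppers.**

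- Dose 1 only: the period covers Day 1 to before Day 29, that is 28 days. 236 − 28 = 208 days uncovered (88.1%).
- Doses 1 and 2 only: the periods cover Day 1 to before Day 57, that is 56 days. 236 − 56 = 180 days uncovered (76.3%).

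**What the IA Day 236 version would add.** The IA Day 85 analysis takes events starting up to Day 85. With dose 3 four days late, period 3 ends on Day 89, so up to 89 − 85 = 4 further days could enter. With dose 3 ten days late it is 95 − 85 = 10 days. Apart from these days and data updates between the two outputs, the two versions have the same onset windows.

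**Whether another table fills the gap.** The other adverse event tables marked for IA Day 236 (14.1.4.1 to 14.1.4.4, 14.1.4.6 to 14.1.4.13 and 14.1.4.48 to 14.1.4.59) accumulate from Day 1. None is limited to late onset. Subtracting subject counts at IA Day 85 from those at IA Day 236 does not give the number of subjects with an event in the added time, because a subject with events both before and after Day 85 is counted once in each output.

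**The case against.** The strongest case on the other side is that this is a presentation choice in one secondary table. Section 1.3.2 defines the unsolicited AE, SAE and AESI endpoints as frequencies over the entire study, and cumulative tables are what such endpoints call for. A vaccination period that ends 28 days after a dose is coherent in itself. Nothing in the objectives asks for post-vaccination follow-up as a separate stratum.

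Much of this stands, and it rules out several stronger readings that a reader might infer:

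- *That late events drop out of the analysis.* They do not. They count in the cumulative IA Day 236 tables, and the unsolicited-event listings give the study day of onset.
- *That diary reactions mask late events throughout.* Table 14.1.4.1 has separate unsolicited and AESI rows, and Tables 14.1.4.48 to 14.1.4.59 exclude diary reactions.
- *That every other IA Day 236 safety table is cumulative.* This is true of the adverse event tables only; most laboratory and vital-sign tables are by visit.
- *That late events can be found only in listings.* Section 6.1.2.1 counts events in each category in the severity and causality tables. Differencing Tables 14.1.4.54 to 14.1.4.59 between the two interims therefore gives late event counts by group for unsolicited, medically attended unsolicited and AESI events, apart from data updates.
- *That the follow-up will never be shown separately, up to Month 12.* Section 2.15 refers to a separate SAP for the final analysis, which is not at hand.

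The percentages above are also shares of calendar time. They are not shares of events or subjects, and the number of early stoppers is not given.

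What the objection does not answer is that a table planned and tested at IA Day 236 does not cover what its header would say. Differenced event counts also do not give subject-level rates.

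**Conclusion.** The point holds as a mismatch between the period definition in section 6.1.2.3 and the IA Day 236 use of Table 14.1.4.5. On the nominal schedule, 151 of 236 days (64%) belong to no period. The figure is 147 to 155 days with dose 3 within ±4 days, about 180 days for subjects with two doses and about 208 days for subjects with one. No adverse event table planned in this SAP gives subject-level rates by group for that time.

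Severity is minor. No event is lost, no endpoint is left without its table, and no estimate is shown to be biased. The conclusion assumes that the general header rule of section 6.1.2.1 applies to Table 14.1.4.5, as its IA Day 236 mark implies, and it is confined to the two interim analyses.

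**What to change.** Add a follow-up category to section 6.1.2.3: adverse event start more than 28 days after the last vaccination received, up to the data cut-off. Apply it in the same way to subjects who stopped after dose 1 or dose 2. Align the boundary when doing so. For early stoppers the current rule ends the period before the 28-day date, whereas period 3 includes that date; without alignment, an event on exactly that day in an early stopper would fall in neither category.

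State the denominator as subjects still under observation after that point. Sections 6.1.2.1 and 6.1.2.3 tie percentages to the treatment group total only for tables not split by time period, so the by-period denominator for unsolicited events needs stating in any case.

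Show the category as one extra block in Table 14.1.4.5 at IA Day 236, for the unsolicited AE, related, severe, SAE, medically attended and AESI rows, with confidence intervals.

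The cost is a short addition to section 6.1.2.3 and one block in a planned table, using data already collected. The downside is a few more comparisons with low counts, which may be shown descriptively without tests.
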